2.1. Provide

2.1.1. the mode of data collection, e.g. telephone, in-person, questionnaire, interviews: **Interview tools include: The Structured Interview for DSM-IV-TR Axis I Disorders, Clinical Trials Version (SCID); World Health Organization Disability Assessment Scale v. 2.0 (WHODAS), Work Behavior Inventory (WBI), Specific Level of Functioning Scale (SLOF), Brief Negative Symptom Scale (BNSS), Scale for the Assessment of Positive Symptoms (SAPS), the Check-In, and the Work Readiness Assessment** The 15-minute check-in is a tool developed by the research team to capture information about medications and services being received outside of the study, and will include measures of workforce participation. Training of assessors on the clinical interview will follow the UCLA model of initial training, competency (ICC \rightarrow .80 with a minimum of 10 cases), and prevention of rater drift (sessions every 6 months).

Questionnaires include: Dysfunctional Attitude Scale (DAS),⁶³ Asocial Beliefs Scale (ABS),⁶⁴ Beck Self-Esteem Scales – Short Form (BSES-SF),⁶⁵ the Quality of Life Inventory (QOLI),⁶⁶ and the Beck Cognitive Insight Scale (BCIS).⁶⁷

Cognitive and Functional Tests include: the Computerized Neurocognitive Battery (CNB), the Brief Cognitive Assessment Tool for Schizophrenia (B-CATS), and the USCD Performance-Based Skills Assessment – Brief (UPSA-B).

Specific Levels of Functioning Scale (SLOF).⁵⁶ The SLOF is a self-report behavioral rating scale used to assess mentally ill patients' level of functioning in the community and in mental hospitals. The 30-item scale emphasizes subjects' everyday behaviors rather than emotional or mental capacity, and it focuses on subjects' tangible strengths and skills rather than on subjects' weaknesses. Subjects rate their typicality of certain behaviors and self-sufficiency regarding basic tasks on a 5-point scale, in the areas of interpersonal relationships, social acceptability, activities, and work skills. A high total suggests a higher level of functioning in the subject, while a low total suggests relatively lower functioning. The SLOF is considered to be one of the best scales for measuring functional outcomes in terms of reliability, convergent validity, sensitivity, and practicality.⁶⁰

World Health Organization Disability Assessment Schedule 2.0 (WHODAS).⁵⁶ The WHODAS is an interviewer-administered assessment designed to determine the level of functioning in subjects with schizophrenia. The WHODAS measures a number of areas, including cognition, mobility, self-care, sociability, life activities, work/school activities, and participation. Each item is measured on a 5-point scale, with higher totals indicating higher levels of dysfunction. Schennach-Wolff et al.⁶¹ found the WHODAS to have predictive validity for early response, response, remission, and symptomatic outcome.

Brief Negative Symptom Scale (BNSS).⁵⁷ The BNSS is a 13-item interviewer-scored instrument for assessing the negative symptoms of schizophrenia. Each item is rated on a 7-point scale: "Normal/No Impairment" (0), "Questionable/Very Slight Impairment" (1), "Mild/Mild

Deficit" (2), "Moderate/Moderate Deficit" (3), "Moderately Severe/Moderately Severe Deficit" (4), "Severe/Marked Deficit" (5), "Extremely Severe/Severe Deficit" (6). The items are organized into six subscales: Anhedonia (3 items), Distress (1 item), Asociality (2 items), Avolition (2 items), Blunted Affect (3 items), and Alogia (2 items). The total score is the sum of the 13 items, with the total possible score ranging from 0 to 78. Higher scores are indicative of greater negative symptomatology.

(<http://www.bhrm.org/guidelines/motiveint.pdf>). It is comprised of two scales: the Understanding of Benefits scale and the Work Motivation scale. Participants are asked to rate items on a 3-point scale (i.e., "disagree," "not sure," "agree") regarding their understanding of benefits, and a 4-point scale (i.e., "disagree," "somewhat agree," "mostly agree," "strongly agree") regarding their motivation to work. Assessors will use this data to determine a participant's overall work readiness on the following scale: Pre-contemplation about working, Contemplation for

working, Determination/preparation for working, Active stage of job seeking, and Maintaining job seeking activities or working.

Risk Assessment. The Risk Assessment is a tool developed by the study team to evaluate the potential risks (to the participant and study staff) in enrolling the participant into phase 2 of the research study. The risk assessment will be completed as part of the baseline/screening assessment, and then as clinically indicated throughout study participation (e.g., when a subject moves, after an inpatient hospitalization, etc.).

Questionnaires. Belief endorsement and quality of life, questionnaires include: Dysfunctional Attitude Scale (DAS),⁶³ Asocial Beliefs Scale (ABS),⁶⁴ Beck Self-Esteem Scales – Short Form (BSES-SF),⁶⁵ the Quality of Life Inventory (QOLI),⁶⁶ and the Beck Cognitive Insight Scale (BCIS).⁶⁷

Dysfunctional Attitude Scale (DAS).⁶³ The DAS consists of 40 statements rated on a 7-point scale: “Agree Totally” (7), “Agree Very Much” (6), “Agree Somewhat” (5), “Neutral” (4), “Disagree Somewhat” (3), “Disagree Very Much” (2), and “Disagree Totally” (1). Participants are instructed to select the option that describes how they think most of the time. Sample items include: “If I do not do as well as other people, it means I am an inferior human being”; “If I fail at my work, then I am a failure as a person”; “If I fail partly, it is as bad as being a complete failure”; “If you cannot do something well, there is little point in doing it at all”; “Making mistakes is fine because I can learn from them (reverse keyed).” The DAS is composed of two subscales: Defeatist Performance Attitudes and Dysfunctional Need-for-Acceptance attitudes. The DAS can be reliably administered and its utility in outpatient samples diagnosed with schizophrenia has been established.²²

Asocial Beliefs Scale (ABS).⁶⁴ The ABS is composed of 15 items self-reported as “True” or “False” (scored “1” or “0”) that tap attitudes and preferences related to spending time with other people. Sample items include: “I prefer watching television to going out with other people,” “people sometimes think I am shy when I really just want to be left alone,” and “I could be happy living all alone in a cabin in the woods or mountains.” In both patient and control populations, the ABS has been shown to be internally consistent and have high test-retest reliability.⁶⁸ Grant and Beck have shown that these items, which are a subscale of the larger Revised Social Anhedonia Scale (RSAS), predict current and future social functioning.³¹

Beck Self-Esteem Scales – Short Form.⁶⁵ Beck Self-Esteem Scales – Short Version.⁶⁵ The BSES-SF is a 12-item questionnaire that assesses beliefs about the self and others’ impressions of the self. Domains queried include superior/inferior, likeable/unlikeable, strong/weak, secure/vulnerable, efficient/helpless, and powerful/powerless. Responses are made to each bipolar set of adjectives on a 10-point scale (anchors are “very much”, “average”, and “very much”). Modifications to the original form include: (1) the measure was shortened to capture the essence of self-esteem, and (2) seven of the twelve adjectives have been modified to better suit this population based on clinical experience.

Quality of Life Inventory (QOLI).⁶⁶ The QOLI consists of 32 self-reported items that tap subjective functioning. Participants are presented with descriptions of 16 life domains: health, self-esteem, goals-and-values, money, work, play, learning, creativity, helping, love, friends, children, relatives, home, neighborhood, and community. For each domain, the subject makes an importance judgment on a 3-point scale -- “Not Important” (0), “Important” (1), “Very Important” (2) -- and a satisfaction judgment on a 6-point scale -- “Very Dissatisfied” (-3), “Dissatisfied” (-2), “Somewhat Dissatisfied” (-1), “Somewhat Satisfied” (1), “Satisfied” (2), “Very Satisfied” (3). QOLI scores for each domain are determined by multiplying the importance rating by the satisfaction rating. The total QOLI score is the sum of the 16 individual domain scores; higher scores reflect higher reported quality of life.

Beck Cognitive Insight Scale (BCIS).⁶⁷ The BCIS is a 15-item measure of two components (factors) of cognitive insight—the capacity and willingness to observe one’s experiences and consider alternative explanations (self-reflectiveness) and the overconfidence in the validity of one’s beliefs (self-certainty). Sample items include, “There is often more than one possible explanation for why people act the way they do” and “My interpretations of my experiences are definitely right.” In the original study with inpatients of varying diagnoses, the BCIS showed adequate convergent and discriminant validity and internal consistency ($\alpha = .60-.68$). The original psychometrics and factor structure have now been replicated several times.⁶⁹ Taken together, the research on the BCIS suggest that cognitive insight has important clinical significance for people with schizophrenia, that it may be a mediating variable in cognitive therapy for the disorder, and that it should therefore be assessed and addressed in clinical trials.⁶⁹

Collection of information from the Work Behavior Inventory (WBI).⁵⁵ The WBI is a 35-item scale specifically designed to assess the work behaviors of individuals suffering from severe mental illness. The WBI is completed as a routine standard of care measure during Supported Employment procedures. As part of usual care, the SE Specialists observes the patient in his/her work setting and also speak to the subject’s supervisor (when the veteran allows this). As part of the research study, we will collect information from the WBI at the time of the baseline and follow-up assessments. The measure will have a value of ‘0’ at points in which the participants are not working. WBI data may be missing if research participants refuse to allow the SE specialist to observe at the worksite and/or speak to employers. Data from the WBI will be analyzed along with other research data whenever available. The WBI is broken down into specific areas, including social skills, cooperativeness, work habits, work quality, and personal presentation. Each item is scored on a 5-point scale, with higher totals indicating stronger work performance. The WBI has been found to have good validity and reliability⁵⁵ and predicts vocational outcomes and productive activity after discharge from rehabilitation.

Performance measures

a) Cognitive

The Computerized Neurocognitive Battery (CNB). The CNB, developed by Ruben Gur and colleagues, is widely used and validated.⁷⁰ The version we will use evaluates both accuracy and speed of performance in the following 5

domains: abstraction and mental flexibility (Penn Conditional Exclusion Test), attention and working memory (Letter-n-Back), spatial memory (Visual Object Learning Test [VOLT]), spatial processing (Computerized Judgment of Line Orientation), and sensorimotor dexterity (Computerized Finger-Tapping Task and Motor Praxis test). Participants will be given standard instructions and practice trials with feedback to assure comprehension. Collected data are uploaded automatically to the VA MIRECC secure server using PGP encryption and reviewed for validity. Accuracy and response time for each trial are recorded and the domain scores for accuracy and speed are available in a relational database. The scoring code has been validated against manually scored tests. This procedure is fully automated.

Brief Cognitive Assessment Tool for Schizophrenia (B-CATS)⁷¹: The B-CATS is a 10-12 minute measure of global cognitive function designed for clinicians to administer and interpret. The B-CATS is composed of 3 neurocognitive tests, Trail Making Test (parts A and B), animal fluency, and Digit Symbol.

b) Functional capacity

The UCSD Performance-Based Skills Assessment-Brief (UPSA)⁷² : The UPSA assesses functional capacity -- that is, the expected ability of subjects to function in a variety of real-world settings. This measure assesses skills in two areas: a) Communication (making phone calls, making emergency calls, rescheduling a medical appointment, and others), and b) Finance (e.g. counting change, writing checks, and paying bills). The brief UPSA (10 -15 min) has been shown to correlate at 0.91 with the scores on the full UPSA.⁷³

- 2.1.2. the precise plan for how data is to be collected or acquired At the baseline assessment interview, a member of the research team (PI, Co-I, or research coordinator) will administer a comprehensive, face-to-face interview that allows for a reliable diagnosis of schizophrenia and queries patient psychosocial functioning levels, symptomatology, substance use, and service usage. At other assessments, the independent assessors will perform semi-structured interviews, collect questionnaire data, and administer cognitive and performance tests.
- 2.1.3. exact location where data will be collected, In a pre-arranged 2nd floor MIRECC interview room (B228).
- 2.1.4. exact location where data entry will take place. In the pre-arranged 2nd floor MIRECC interview room (B228) and the research coordinator's and independent assessors' cubicles in the 2nd floor MIRECC (B228).
- 2.1.5. the "title" of individual(s) collecting the data and analyzing the data, e.g. principal investigator, research coordinator. **Principal Investigator, Co-Investigators, Research Coordinator, Independent Assessors.**
- 2.2. Provide a time line for each aspect of the study. **Assessment sessions will occur at baseline, and at 6, 12, and 18 months after treatment groups begin. Check-ins will occur at baseline, and then every 3 months after treatment groups begin.**

Subjects in the iCBT condition will receive weekly or twice weekly group sessions for 12 months. It incorporates cognitive remediation strategies, and a specific computerized cognitive remediation 4-month block (see below). Subjects assigned to usual care will continue to receive usual care for 12 months. Subjects in both conditions will participate in the existing SE program at CMCVAMC. All participants will continue to receive any services (medical, psychiatric, case management) they were already receiving. The primary outcome measure will be the indices of workforce participation (jobs attained, hours per week, average days worked while employed, weeks employed, total income for the reporting period) . Secondary outcomes measures will be the total score on the Work

Behavior Inventory (WBI) and the total score on the Specific Levels of Functioning inventory (SLOF) measured at 6 months, 12 months, and 18 month post-treatment follow-up.

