Eligible subjects who give a second informed consent will be randomly assigned to receive either iCBT or to usual care. All randomized participants will enter into supportive employment at the CMCVAMC. iCBT will be delivered as a group therapy for 12 months of weekly or biweekly sessions (see below). iCBT sessions will take approximately 1 hour. Blind, reliable independent assessors will reassess participants every 6 months after participants begin treatment groups over an 18-month participation period, producing mid-treatment (6 month) end-of-treatment (12 month), and post-treatment (18 month) assessments. Follow-up assessment procedures will take approximately 3-4 hours. The Research Coordinator will conduct a 15-minute Check-In at baseline to gather information about medications and services being received outside of this research study; the Supported Employment Specialists or Independent Assessors will conduct the 15-minute Check-In every 3 months after participants begin treatment groups (i.e., at 3-, 6-, 9-, 12-, 15-, and 18-months). The SE Specialists will also conduct the assessment of employment variables at these Check-Ins using the Workforce Participation form using an informal interview assisted by the use of a calendar and review of holidays and other activity anchors, supplemented by the ongoing assessment they conduct as part of the SE activities.

We are proposing a prospective randomized controlled trial with participants recruited from the CMCVAMC. We will randomize 96 patients (48 patients per condition). Independent assessors will be blinded to participant treatment group allocation. Assessment sessions will occur at baseline, and at 6, 12, and 18 months after therapy groups begin; brief check-ins will occur at each assessment session, and also at months 3, 9, and 15 after therapy groups begin.

Subjects in the iCBT condition will receive weekly or twice weekly group sessions for 12 months. iCBT follows a treatment manual developed by Perivoliotis, Grant, & Beck. The manual details the approach (engagement, behavioral activation, cognitive remediation/restructuring, maintenance) and individualized treatment planning. It also describes strategies and techniques to deal with positive and negative symptoms, mood symptoms, and suicidality. Included in these strategies are mindfulness exercises, designed to assist the participant in identifying feelings and biological processes that accompany a stimulus (i.e.,

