This study is powered to detect a clinically significant difference between iCBT and the usual care conditions. Meta-analysis of medical and behavioral outcomes indicates that a medium effect-size between conditions will have a significant impact on quality of life. In a previous study we observed an average effect of about $d=0.55$ SD. To allow for a somewhat smaller effect in this proposed study, we design our study to have 80% power to detect clinically significant effect of $d=0.5$ SD. In the pilot data, we found a within-subject correlation structure consistent with a stationary autoregressive process with correlation parameter 0.4. We also assume a dropout rate of 20% for these power calculations. With these assumptions on effect size, covariance structure, and dropout rates, and with a two-sided alpha level of 0.05, the methods of Hedeker et al.⁸⁶ estimate that a sample size of 48 subjects per group will provide 80% power for the test of our primary hypothesis.

We believe that this is a conservative estimate, based on the larger effect size observed in our prior study, and the higher than expected dropout rate used in the calculation. In addition, our analyses will use the baseline measure of Psychosocial Functioning as a covariate, which should reduce the standard errors in our test, and therefore increase the smallest detectable effect size.

4.2. Define plans for data and statistical analysis, including key elements of the statistical plan, stopping rules and endpoints.

Planned Analyses

(i) Overview

Logistic, log-linear and linear random effects models (hierarchical regression models) will be implemented with random intercepts and slopes for longitudinal binary, count, and continuous outcomes, respectively. These models will contain separate main effects for change from baseline to each follow-up visit at 6, 12, and 18 months, main effect for the treatment, and interactions between the visit and treatment indicator variables. For each of the primary (workforce participation indices) and the secondary (Work Behavior Inventory, Specific Levels of Function) outcomes, separate intent-to-treat (ITT) tests and estimates (with 95% confidence intervals) of randomized group contrasts at 6, 12, and 18 months will be obtained from the estimates of the respective time-treatment interactions.

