While the present study is designed to minimize lost observations, the proposed random effects or hierarchical regression approach is superior to last observation carried forward in minimizing bias and Type 1 error and inferentially equivalent to multiple imputation.⁷⁹ To assess the sensitivity of treatment effect estimates to missing data, we will compare the results under the above hierarchical regression models with those based on shared parameter models that account for informative missingness that is dependent on unobserved outcomes through a latent variable.⁸⁰ If the results between the two approaches are similar then we will present the proposed hierarchical regression models as robust to informative missing data; otherwise we will note that the results may be

sensitive to informative missing data and augment them with those based on the shared parameter model.

(ii) **Work outcome.** The primary trial outcome measure, workforce participation (composite index) at 6, 12 and 18 months analyzed in the manner described above. A significant ITT difference on the total WBI score across 6 and 12 months would support the hypothesis that iCBT is more efficacious than usual care at improving work outcomes by the end of treatment (Primary Aim 1). Similarly, WBI score at 18 months is a secondary outcome, and a separate ITT effect on work outcomes at 18 months with the respective month-treatment interaction in favor of iCBT would support the hypothesis that it promotes better work outcomes than usual care during the 6 months after the completion of treatment (Secondary Aim 2).

(iii) **Functional outcome.** The second trial outcome measures include the Work Behavior Inventory and the total score on the Specific Levels of Functioning Inventory (SLOF) at 12 months A significant ITT difference on the WBI and the total SLOF score across 6, 12 months would support the hypothesis that ICBT is more efficacious than usual care at improving functioning by the end of treatment (Secondary Aim 1). Similarly, WBI and SLOF total score at 18 months is a secondary outcome, and the separate ITT effects on functioning at 18 months with the respective month-treatment interaction in favor of iCBT would support the hypothesis that it promotes better functioning than usual care during the 6 months after the completion of treatment (Secondary Aim 3).

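### A refused WBI score implies a working participant, yet no planned WBI analysis is stated to use the employment status recorded at the same visit, so known workers' missing scores are predicted partly from non-workers' zeros

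*Combined protocol and SAP*

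**What the plan says.** **Scoring and missingness (Section O.2.1.1, Work Behavior Inventory).** Non-workers have an observed score: "The measure will have a value of ‘0’ at points in which the participants are not working". The one WBI-specific reason given for missing data is refusal: "WBI data may be missing if research participants refuse to allow the SE specialist to observe at the worksite and/or speak to employers". The only handling rule is "Data from the WBI will be analyzed along with other research data whenever available". The scale has 35 items; "Each item is scored on a 5-point scale, with higher totals indicating stronger work performance".

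**Employment (Section O.1.1 and Table 1).** "The SE Specialists will also conduct the assessment of employment variables at these Check-Ins using the Workforce Participation form". The form is filled in by informal interview with a calendar, supplemented by what the specialists learn in routine SE work. It is collected at baseline and every 3 months to month 18, and so at every WBI visit.

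**Models (Statistical Analysis 4.2 (i)).** Random-effects models with random intercepts and slopes contain visit effects, a "main effect for the treatment, and interactions between the visit and treatment indicator variables". Baseline variables that differ significantly between arms are added as covariates. Employment at the visit is not named.

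**Missing data (same section).** The random-effects approach is described as "inferentially equivalent to multiple imputation". Its results are to be compared with "shared parameter models that account for informative missingness that is dependent on unobserved outcomes through a latent variable". If the two disagree, the plan will say so and report both.

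**The concern.** The plan foresees a type of missing WBI value that identifies the participant as working, and it collects the variable that shows this. It then analyzes WBI with a model that sees only visit, arm, imbalanced baseline variables and the participant's other WBI scores. Observed WBI at a visit mixes zeros from non-workers with scores from workers. A normal model that does not know who is working predicts a refused score from that mixture, although the score must come from the worker part of it.

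The stated equivalence to multiple imputation does not cover this. It holds when both methods use the same variables. It does not hold against an imputation that uses recorded employment, which is related both to missingness and to the outcome.

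WBI is a named secondary outcome, and Section 4.2 (ii) also ties a WBI difference across 6 and 12 months to Primary Aim 1. Unequal refusal between arms is plausible: the employment specialists who observe at the worksite also deliver iCBT, so iCBT participants have a relationship with the observer that usual-care participants lack.

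**Working it through.** The documents give no employment rate, refusal rate or worker mean for WBI, so there is no stated figure to reproduce. The 48 per group and 20% dropout in Section 4.1 are used below only to judge cell sizes.

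**Assumptions (not in the documents).** Mean WBI among workers m = 120. If items are scored 1-5 (the anchors are not stated), a worker's total lies between 35 and 175, far from 0. Proportion working p, refusal among workers q, refusal unrelated to score.

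**Formulas.** True arm mean = p·m. Mean of observed scores, among those followed = p(1-q)m / (1-pq), because non-workers (1-p) and consenting workers p(1-q) are observed.

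**Equal refusal in both arms**

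| Working, iCBT vs usual care | True difference | Observed, q = 20% | Observed, q = 30% |
|---|---|---|---|
| 45% vs 25% | 24.0 | 22.2 (-7.5%) | 21.0 (-12.5%) |
| 40% vs 25% | 18.0 | 16.5 (-8.5%) | 15.5 (-14.0%) |
| 60% vs 40% | 24.0 | 23.7 (-1.2%) | 23.3 (-3.0%) |
| 80% vs 60% | 24.0 | 26.0 (+8.2%) | 27.0 (+12.3%) |

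For example, the first row at q = 20%: 0.45×0.8×120/0.91 = 47.5 and 0.25×0.8×120/0.95 = 25.3, a difference of 22.2. Each arm mean is too low (true values 54 and 30), but the change in the difference depends on the employment level.

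**Unequal refusal, no true effect.** With 35% working in both arms the true mean is 42.0 in each. Observed means are 39.2 at q = 10%, 32.9 at 30% and 29.3 at 40%. The spurious difference is 6.3 or 9.9 points. The SD from the zero/120 mixture is 120×√(0.35×0.65) = 57, so this is 0.11 or 0.17 SD.

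**Does the likelihood model repair this?** The formula describes raw observed means, so a large simulation was used (three visits, normal maximum likelihood with unstructured covariance in each arm, as a stand-in for the planned model).
- Equal refusal of 10-40%: the 12-month difference (true about 24) changes by -3% to -27% at 20% vs 40% working (usual care vs iCBT), and by about 0% to -14% at 40% vs 60%.
- Refusal of 20% in usual care and 40% in iCBT: -27% to -50%. The reverse: +6% to +28%.
- No true effect, 35% working, refusal 10% vs 30-40%, workers' SD 20: about 5-9 spurious points if refusal varies by visit, and 7-11 if the same people always refuse.

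The model recovers some of the loss when refusal comes and goes, and essentially none when it is persistent. Filling refused scores from observed workers in the same arm and visit returned the true difference to within 0.1 point in every scenario with a true effect. That result depends on refusal being unrelated to score.

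**Cell size.** 48 × 0.80 = 38.4 followed per arm. At 25% working that is 9.6 workers, of whom 7.7 have a WBI score at 20% refusal and 6.7 at 30%.

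**The case against.** **Dropout also makes WBI missing.** A reader might infer that WBI is missing only for workers. The documents do not support that: Section 4.1 assumes 20% dropout and Section 4.2 expects some lost observations. Refusals under the equal-refusal assumptions with 25-45% working are 5% (25% × 20%) to 13.5% (45% × 30%) of those followed. The point is therefore limited to refusals among participants still in follow-up. If non-workers drop out more often, which the documents do not say, missing zeros would push the means the other way.

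**Refusing one source need not lose the score.** The text allows refusal of observation, of employer contact, or of both. This affects how often scores are lost, not what a lost score implies.

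**No fixed direction.** A reader might infer that equal refusal always dilutes the effect. The table shows otherwise: dilution at employment rates below about half, almost none around half, inflation above it.

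**Size against noise.** With SD 57 and 38.4 per arm, one visit's difference has a standard error of 57×√(2/38.4) = 13 points. The equal-refusal shift at 40-45% vs 25% working (1.5-3.0 points) is 0.1-0.2 of that. This stands. The unequal-refusal case is the more material one, and it rests on a plausible mechanism, not on data.

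**The plan has a sensitivity analysis.** The shared-parameter model can link missingness to a higher underlying WBI, and the plan commits to disclosing disagreement. That helps, but it works through a latent variable when the relevant variable is recorded. Nor is the sentence on multiple imputation an error in itself: with the same variables in both methods it is an ordinary statement.

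**Conclusion.** The concern holds for refusal-type missingness among participants still in follow-up. A refused score implies a job, employment is recorded at the same visits, and no planned WBI analysis is stated to use it. Refusal by itself lowers the arm means; the treatment difference can be biased in either direction, and hardly at all when refusal is equal, varies by visit and employment is near 50%.

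On observed data, equal refusal of 20-30% changes the difference by between -14% and +12% across the employment rates tried. Refusal of 10% vs 30-40% with no true effect creates about 6-10 points (0.1-0.17 SD). All of these figures rest on an assumed worker mean of 120, assumed employment and refusal rates, and refusal unrelated to score.

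This should be corrected before analysis. It concerns WBI only, and it does not show that the trial's WBI result will be biased by any particular amount.

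**What to change.** In Section 4.2, add a WBI-specific rule:

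1. Use multiple imputation with employment status at the visit, from the Workforce Participation form, as an auxiliary variable. Do not add employment as a covariate to the ITT model, since it is measured after randomization and may itself be affected by treatment.
2. Impute refused scores of participants known to be working from observed workers. Use a small model pooled over visits and arms with an arm term, since arm-by-visit cells may hold only 7-8 observed workers. A two-part model (working or not, then score if working) is an alternative.
3. For dropouts whose employment is unknown, impute employment status first, then WBI given that status.
4. Keep the shared-parameter model as a sensitivity analysis, because refusal may depend on work performance and imputation from other workers would not correct for that.
5. Limit the statement on equivalence to multiple imputation to imputation that uses the same variables.
6. Report the number of WBI refusals by arm and visit.

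The cost is SAP wording and a little more analysis work with data already collected. The downside is that the main WBI result then relies on refusal being unrelated to score among workers.
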